## **4.2. Secondary Endpoints**

### **4.2.1. Secondary Safety Endpoints**

Secondary endpoints include incidence of other device-related adverse events and all other adverse events long-term. Patients will be evaluated by physical examination, CT scan, ultrasound, and biomarker cancer antigen CA-125. Please also refer to Section 7 (anticipated or potential adverse events).

### **4.2.2. Secondary Performance Endpoints**

Secondary performance endpoints include semi-quantitative scoring of disease focalization based on direct visual assessment, CT scan and ultrasound at the time of device removal. In addition, a microscopic assessment will be performed during explant, including cytologic assessment of any ascites present, cytologic assessment of peritoneal washings, if indicated, and a minimum of two (2) peritoneal biopsies from designated locations, if indicated.

## **5. SUBJECT SELECTION**

### **5.1. Inclusion Criteria (IC)**

Candidates for the study must meet ALL of the following inclusion criteria:

1. Is a female  $\geq 18$  years old.
2. Presents with a diagnosis of Stage IIIc or IV ovarian cancer.
3. Presents with high-grade serous carcinoma.
4. Has one of the following:
  - a. Stage IIIc disease and visible residual tumor  $\leq 1$  cm after primary tumor debulking surgery.
  - b. Stage IIIc or Stage IV disease and three or four cycles of neoadjuvant chemotherapy and complete resection after interval tumor debulking surgery.
  - c. Stage IIIc or Stage IV disease and three or four cycles of neoadjuvant chemotherapy and visible residual tumor  $\leq 1$  cm after interval tumor debulking surgery.
5. ECOG performance status of 0 or 1.
6. Is willing to comply with required follow-up study visits.

7. Is willing and able to provide written informed consent.

## **5.2. Exclusion Criteria (EC)**

Candidates for this study will be excluded if ANY of the following conditions are present:

1. Has a life expectancy of <3 months.
2. Is pregnant, as confirmed through a blood test prior to any study procedure, planning on becoming pregnant during the study, or is lactating.
3. Will be receiving intraperitoneal chemotherapy.
4. Has undergone prior treatment with abdominal and/or pelvic radiotherapy.
5. Has significant active concurrent medical illnesses including, but not limited to, ongoing or active infection, symptomatic congestive heart failure, unstable angina pectoris, cardiac arrhythmia, or psychiatric illness/social situations that would limit compliance with study requirements.
6. Presence of central nervous system or cerebral metastases.
7. Recurrent ovarian cancer.
8. Complete resection with no residual tumor after primary tumor debulking surgery.
9. Suboptimal resection with > 1 cm residual tumor after primary or interval tumor debulking surgery.
10. Is simultaneously enrolled in another investigational study.
11. Has a history of cancer within 5 years other than in-situ uterine cervix cancer or non-melanoma skin cancer.
12. Has a known hypersensitivity to carboplatin or paclitaxel.
13. Is concurrently using other antineoplastic agents.

## **5.3. Subject Accountability**

### **5.3.1. Enrolled Subjects**

The point of enrollment starts when the subject provides written informed consent and agrees to participate in the clinical investigation. Subject for whom consent was not obtained prior to participation in the study will not be considered enrolled. No data collected from this "subject" will be included in any analysis.

### **5.3.2. Screen Failures**

A screen failure subject is an enrolled subject who withdraws consent prior to index procedure or is unsuitable for index procedure following the debulking procedure. This subject will be exited from the study once screen failure is confirmed. Screen failure subjects will be recorded in Enrollment and Screening Log. Their signed informed consent forms will be kept in the site's administrative files.

### **5.3.3. Treated Subjects**

A treated subject is an enrolled subject who meets all eligibility criteria, and has been treated. This subject will be followed in accordance with the protocol requirements.

## 6. STUDY PROCEDURES AND ASSESSMENTS

### Schedule of Assessments / Flow Chart:

Examination/ Assessment	Visit 0 Screening Within 21 days	Visit 1 Procedure (D0)	Visit 2 1M (±1W)	Visit 3 3M  (±2W)	Visit 4 6M  (±2W)	Visit 5 9M (±1M)	Visit 6 12M (±1M )	Visit 7 15M (±1M )	Visit 8 18M (±1M )
Signed Informed Consent	X								
Eligibility criteria check	X	X							
Demographics, medical history	X								
Physical examination	X	X	X	X	X	X	X	X	X
Biomarker CA-125	X			X	X	X	X	X	X
CT scan	X			X	X	X	X	X	X
Ultrasound		X	X	X	X	X	X	X	X
PCI 	X	X							
Cytology/biopsy									X 
Pathology (explant)									X 
Adverse events	X	X	X	X	X	X	X	X	X
Concomitant medication	X	X	X	X	X	X	X	X	X

### 6.1. Screening and Baseline Assessments

#### 6.1.1. Informed Consent Process

Investigators will not ask subjects to sign the Informed Consent Form until the clinical investigation has been fully approved by the institution's Ethics Committee (EC) and the Sponsor or their CRO representative has received and reviewed the specific EC-approved Informed Consent form.

When the Investigator has determined the eligibility of a specific subject to enter the clinical investigation, the Investigator will provide an informed consent form to the subject. The Investigator or designee, will discuss and explain the clinical investigation with the subject as follows:

- include a description of all aspects of the clinical study that are relevant to the subject's decision to participate throughout the clinical study,
- avoid any coercion of or undue influence of subjects to participate,
- do not waive or appear to waive subject's legal rights,
- use native language that is non-technical and understandable to the subject or his/her legal representative,
- provide ample time for the subject to consider participation and ask questions if necessary,
- ensure important new information is provided to new and existing subjects throughout the clinical study.

 3M visit must occur after the final chemotherapy infusion in interval debulking patients. The 3M CT scan will serve as the baseline for assessing disease progression for purposes of device removal.

 6M visit must occur after the final chemotherapy infusion in primary debulking patients. The 6M CT scan will serve as the baseline for assessing disease progression for purposes of device removal.

 Peritoneal Carcinomatosis Index.

 To be performed at time of device removal. Device removal may occur earlier if conditions for device removal described in Section 6.2 are met

The Investigator will obtain the signed informed consent form from the subject before performing the implant procedure or any protocol-specific tests. The Investigator will provide subjects with a copy of their signed informed consent form. The Investigator will maintain a copy of the EC-approved Informed Consent Form along with a copy of each subject's signed Informed Consent Form in a designated study file.

If during the debulking procedure, the subject is found not to be eligible for inclusion in the study, the subject should be notified. Reason for ineligibility will be accounted for as "screen failure" and will be documented as such in the Enrollment & Screening log. If the subject has signed the informed consent form, but is found not eligible for inclusion in the study prior to or during the procedure, the subject should receive the appropriate treatment as identified by the clinical investigator.

#### **6.1.2. Screening/Baseline Assessments**

The following screening assessments and tests will be completed within 21 days before the index procedure for those study subjects who continue to be eligible. This set of examinations and tests will be considered the study subject's baseline evaluations:

- Obtain written informed consent. No procedures will be performed without informed consent.
- Check eligibility criteria, including a pregnancy test, if applicable.
- Obtain demographic information.
- Obtain complete medical history.
- Conduct physical examination.
- Collect Biomarker CA-125 level.
- Perform a baseline CT scan of the abdomen, pelvis, and chest.
- Determine Peritoneal Carcinomatosis Index (PCI), if available.
- Record any adverse events.
- Collect concomitant medications information.

#### **6.2. Procedure**

The following assessments and tests will be completed on the day of procedure, prior to the procedure:

- Conduct physical examination.
- Check eligibility criteria Determine Peritoneal Carcinomatosis Index (PCI) pre- and post-debulking.

The following assessments and tests will be completed prior to discharge:

- Perform an abdominal ultrasound (within 24 hours of implant).
- Record any adverse events.
- Collect concomitant medications information.

##### **6.2.1. Debulking Procedure**

Debulking will be performed following the institution's standard protocols. A PCI must be documented pre- and post-debulking. In addition, all residual tumor will be documented on the Case Report Form. If possible, photographs should be taken, documenting the residual tumor.

### 6.2.2. Implant Procedure

Three M-Trap devices will be implanted following the completion of a standard debulking procedure performed following the institution's standard protocols. The three devices will be implanted in the following locations:

- right paracolic (pelvic) gutter;
- left paracolic (pelvic) gutter;
- and behind segment 6 of the liver within the peritoneal cavity.

Prior to use, each M-Trap mesh will be removed from the sterile pouch. Each implant must be submerged completely and soaked for 2 minutes in sterile normal saline in a sterile dish large enough to accommodate the device. The mesh will be placed in the target location and secured using six (6) points of surgical attachment such that the mesh lays flat against the lateral parietal wall, with no wrinkling, dead space, gaps, or other placement deficiencies. A non-absorbable suture, size 2-0, should be used. The suture bite into the mesh should be a minimum of ~0.5 cm from the edge of the mesh. The device should be oriented as necessary to contour to the target anatomy.

Surgery will be completed following the institution's standard protocols. An ultrasound must be performed within 24 hours post-surgery to confirm device placement. Each patient will receive an implant card.

### 6.2.3. Device Removal Procedure

Following completion of chemotherapy treatment, M-Trap devices will be removed under one of following scenarios, whichever occurs first:

- (1) In the event of an adverse event necessitating device removal.
- (2) After disease progression as defined by objective RECIST 1.1 and CA-125 criteria. Both criteria must be met as follows:

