## PROTOCOL SYNOPSIS

Title:	Safety and Performance of Metastatic Tumor Cell Trap Device in Patients with Advanced Ovarian Cancer
Protocol Number:	MTRAP-2016-01
Medical Device:	Metastatic Tumor Cell Trap Device (M-Trap)
Intended Use:	M-Trap is an implantable medical device designed to capture disseminated tumor cells (DTCs). It is intended for use in advanced-stage ovarian cancer patients.
Surgical Use:	Up to three (3) M-Trap devices will be surgically implanted via laparotomy in the right and left paracolic (pelvic) gutters and behind segment 6 of the liver within the peritoneal cavity of the patient at the time of surgical resection. Patients will receive standard chemotherapy with carboplatin and paclitaxel. After completion of chemotherapy, M-Trap devices will be removed via minimally invasive surgery (laparoscopy) following the device removal protocol.
Study Design:	Prospective, multi-center, non-blinded, single-arm study. Safety and performance study conducted in accordance with ISO 14155.
Study Objective(s):	The study objective is to assess the safety and the performance of the MTrap device.  Safety objectives: The primary objective is to demonstrate that the safety of M-Trap, as measured by freedom from device- and procedure-related major adverse events through 6-months post-implantation, is non-inferior to historical controls.  The secondary objective is to collect long-term safety data to support device safety and post-market surveillance. Safety will be evaluated to demonstrate acceptable levels of device-related and procedure-related complications.  Performance objective: The primary objective is to confirm M-Trap performance, as determined by histological evidence of tumor cell capture. The secondary objective is to assess disease focalization with use of the M-Trap device.

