## **Schedule of Assessments / Flow Chart:**

Examination/Assessment	Visit 0 Screening Within 21 days	Visit 1 Procedure (D0)	Visit 2 1 Month (± 1 week)	Visit 3 3 Months  (± 2 weeks)	Visit 4 6 Months  (± 2 weeks)	Visit 5 9 Months (±1 month)	Visit 6 12 Months (±1 month)	Visit 7 15 Months (±1 month)	Visit 8 18 Months (±1 month)
Signed Informed Consent	X								
Eligibility criteria check	X	X							
Demographics, medical history	X								
Physical examination	X	X	X	X	X	X	X	X	X
Biomarker CA-125	X			X	X	X	X	X	X
CT scan	X			X	X	X	X	X	X
Ultrasound		X	X	X	X	X	X	X	X
PCI 	X	X							
Cytology/biopsy									X 
Pathology (explant)									X 
Adverse events	X	X	X	X	X	X	X	X	X
Concomitant medication	X	X	X	X	X	X	X	X	X

 3M visit must occur after the final chemotherapy infusion in interval debulking patients. The 3M CT scan will serve as the baseline for assessing disease progression for purposes of device removal.

 6M visit must occur after the final chemotherapy infusion in primary debulking patients. The 6M CT scan will serve as the baseline for assessing disease progression for purposes of device removal.

 Peritoneal Carcinomatosis Index.

 To be performed at time of device removal. Device removal may occur earlier if conditions for device removal described in Section 6.2 are met.

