## **4.1. Primary Endpoint(s)**

### **4.1.1. Primary Safety Endpoint(s)**

The primary safety endpoint is incidence of device- and procedure-related major adverse events, defined as severe complications based on Clavian Class IV complications, through 6-months post-implantation, including shock, cardiac arrest, myocardial infarction, pulmonary embolism, prolonged intubation, unplanned reintubation, or adverse events leading to removal of the device, including infection, seroma formation, mesh migration, bowel obstruction, adhesions, and local cancer progression through the abdominal wall at M-Trap suture sites.

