### **6.7.2. Withdrawal and Replacement of Subjects**

Subjects may withdraw from the study at any time, with or without reason and without prejudice to further treatment. Patients still implanted at the time of intent of withdrawal will undergo the device removal procedure and associated assessments before being exited from the trial. The reason for withdrawal will be recorded (if given) in all cases of withdrawal. The investigator may discontinue a subject from participation in the study if the investigator feels that the subject can no longer fully comply with the requirements of the study or if any of the study procedures are deemed potentially harmful to the subject. Data that have already been collected on withdrawn subjects will be retained and used for analysis but no new data will be collected after withdrawal.

Withdrawn subjects will not be replaced.

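### Protocol 6.2.3, read literally, makes device removal for an adverse event wait until chemotherapy is complete; this is probably a drafting error, but it should be corrected

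*Protocol*

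**What the plan says.** Protocol 6.2.3 introduces a three-item list with the words "Following completion of chemotherapy treatment, M-Trap devices will be removed under one of following scenarios, whichever occurs first". Item (1) reads "In the event of an adverse event necessitating device removal" and carries no timing of its own. Item (2) is progression by both RECIST 1.1 and CA-125, and item (3) is the 18-month time point.

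The synopsis (Surgical Use) gives the same sequence: "After completion of chemotherapy, M-Trap devices will be removed via minimally invasive surgery (laparoscopy) following the device removal protocol". Footnote 4 to the Schedule of Assessments adds: "Device removal may occur earlier if conditions for device removal described in Section 6.2 are met".

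Two further footnotes to that schedule tie chemotherapy to the visits: "3M visit must occur after the final chemotherapy infusion in interval debulking patients", and "6M visit must occur after the final chemotherapy infusion in primary debulking patients".

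The primary safety endpoint (Protocol 4.1.1, repeated in SAP 2.4.5) runs through 6 months after implantation. Besides the severe complications it lists, it includes "or adverse events leading to removal of the device", with infection, seroma, migration, obstruction and adhesions among the examples.

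**The concern.** The opening clause of 6.2.3 stands in front of the whole list, so grammatically it governs item (1) as well. A site that follows the text would hold an explant that the protocol itself calls necessary until the last infusion has been given. The other course is to explant at once and record the case under some other heading.

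Both outcomes are undesirable. The device has had no earlier clinical use (Protocol 1.4). Its listed risks include infection with abscess, perforation, obstruction and migration (Protocol 7.1.1), and up to eight sites will work from this clause. The rule also conflicts with the endpoint, which counts adverse-event removals in a period during which 6.2.3, as worded, does not provide for them.

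**Working it through.** The point is about wording, and no figure in the plan depends on the clause. The check has three steps.

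**1. Does any other text lift the condition from item (1)?**

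- *Synopsis, Surgical Use:* same order, with no exception for adverse events.
- *Schedule footnote 4 (repeated in Protocol section 6 and SAP 1.3.3):* allows removal before 18 months, but only under the conditions of Section 6.2. That leads back to the same opening clause.
- *Protocol 1.2 and 2, SAP 1.3.2:* link removal to recurrence and do not mention adverse events.
- *End of Protocol 6.2.3:* keeps patients in follow-up to 18 months even if the device came out sooner. It does not say that sooner may mean during chemotherapy.
- *Protocol 6.7.2:* "Patients still implanted at the time of intent of withdrawal will undergo the device removal procedure". This can happen during chemotherapy, but the patient then leaves the trial and no new data are collected.
- *Protocol 11.3:* allows for departures from the plan to protect a patient in an emergency, but treats them as deviations to be notified to the sponsor.
- *SAP 2.4.7:* censors time to recurrence at a removal for another reason before 18 months. This is a rule for analysis and permits nothing clinically.

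None of these expressly allows an adverse-event explant during chemotherapy with the patient remaining on study.

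**2. What does the opening clause do for the other two items?** Very little. The RECIST part of item (2) is measured from a baseline that 6.2.3 defines as the follow-up time point after chemotherapy. Item (3) falls a year after the later of the two visits by which chemotherapy is meant to be finished. The clause therefore restricts mainly item (1), the one item for which delay makes no clinical sense. That supports reading it as a drafting slip.

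**3. How much of the endpoint period could be affected?** The inputs are the visit windows (3 and 6 months, each ±2 weeks) and the endpoint window in SAP 2.5 (6 months ±2 weeks). Taking 3 months as 13 weeks and 6 months as 26 weeks:

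- Endpoint window: 26 + 2 = 28 weeks.
- Interval debulking, last infusion before the 3-month visit: at most 13 + 2 = 15 weeks; 15/28 = 0.54.
- Primary debulking, last infusion before the 6-month visit: at most 26 + 2 = 28 weeks; 28/28 = 1.00. Since the infusion has to precede the visit, this means nearly all of the window.

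These figures assume that chemotherapy ends just before the visit and that the visit is held at the late edge of its window. Earlier completion shortens the restricted period. Later completion lengthens it, and SAP 2.4.4 allows for that by tabulating reasons for incomplete chemotherapy at follow-up. The figures therefore describe the planned schedule and are not strict upper bounds.

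**The case against.** The strongest reply is that nobody would read the clause that way. It says when devices are to come out and nowhere forbids earlier removal. An event that necessitates removal is by its nature not one to defer. The endpoint counts such removals from implantation onward without reference to chemotherapy, which is good evidence of what was meant. Protocol 6.7.2 also lets the investigator discontinue a patient when study procedures are thought harmful, and the device is then taken out before exit.

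Much of this stands. A reader might infer that the sponsor intended to postpone necessary explants, or that patients would in fact be left with a harmful implant. The documents do not support either inference. What remains is that the operative rule says one thing and the endpoint presupposes another, and that the routes around the rule are poor. Withdrawal ends data collection, although 6.2.3 wants follow-up to 18 months after an early removal. The emergency route records correct care as a deviation.

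Two further inferences are tempting. One is that the primary test is biased. The rate of adverse-event removals and the actual end dates of chemotherapy are not given, so neither the size nor the occurrence of a bias can be shown. The share of the window that is restricted does not measure harm. The other is that SAP 2.5 would miss an event whose explant falls after 6 months. It would not need to: the derivation there dates the event, not the explant, and relies on a flag for whether the event meets the endpoint definition. An in-window event with a later explant can already be counted.

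**Conclusion.** The inconsistency is real and should be corrected. Read literally, Protocol 6.2.3 makes adverse-event removal conditional on completed chemotherapy, the synopsis repeats the order, and nothing exempts it for a patient who stays on study. The wording is certain. The view that it is a drafting error is a judgement that rests on the endpoint definition and on how little the clause does for the other two scenarios.

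On the planned schedule the conflict spans about half of the endpoint period in interval-debulking patients and nearly all of it in primary-debulking patients, on the timing assumptions set out above. The practical consequence is ambiguity in a safety rule, with delay or misclassification of a necessary explant if a site follows it to the letter. There is no demonstrated effect on the primary analysis.

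**What to change.** In Protocol 6.2.3, take the chemotherapy condition out of the opening sentence and attach it to scenarios (2) and (3) only. In scenario (1), put *At any time after implantation,* in front of the existing words. In the synopsis, begin the removal sentence with *After completion of chemotherapy, or at any earlier time if an adverse event necessitates it,* and leave the rest as it is.

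Schedule footnote 4 then works unchanged, because the Section 6.2 conditions to which it refers will include early adverse-event removal. SAP 2.5 needs no new text. A sentence there that counted any adverse event followed by explant could drop the requirement that the event be related to the device or procedure, and so change the endpoint.

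The cost is one edited clause in 6.2.3 and one in the synopsis, submitted through the amendment route in Protocol 11.2. No visit, assessment or form changes. The 20 evaluable patients, the one-sided 5% level, the 25% margin and the stated power are unaffected.
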